10.2.3 Descriptive Analysis

Independently of results on primary and key secondary endpoints, descriptive in nature analyses will be performed on all secondary endpoints (section 3.2.2) at each available timepoints by means of descriptive statistics.

In case of continuous measures, analyses will be provided for baseline visit, each post-baseline visit, and their change from baseline. Comparisons between treatments will be performed using two-sample t-test (assuming unequal variances) or, if the required assumptions are not met, the two-

sample Mann-Whitney U test will be used. Assumption of normal distribution of endpoints for continuous data will be assessed by a visual inspection of distribution.

In case of categorical variables, shift tables versus baseline will be summarized for all post-baseline visits, and the Fisher's Exact test will be performed.

The following graphical representations will be provided by treatment:

- Schirmer I test Observed Mean (\pm SEM) and Mean change from baseline (\pm SEM) at each timepoint.
- Observed percentage of patients with Schirmer I test $>10\text{mm}/5\text{min}$ at each timepoint.
- SANDE global score Observed Mean (\pm SEM) and Mean change from baseline (\pm SEM) at each timepoint.
- Cornea and conjunctiva vital staining total score Observed Mean (\pm SEM) and Mean change from baseline (\pm SEM) at each timepoint.
- TFBUT Observed Mean (\pm SEM) and Mean change from baseline (\pm SEM) at each timepoint.

11. Evaluation of Safety

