3.2.2 Secondary

Objective(s)	Endpoint(s)

To compare the efficacy of cenegermin vs. vehicle in Schirmer I test at week 4, 8, 12 and 16 by testing the superiority.	
Change from baseline in Schirmer I test [Time frame: week 4, 8, 12 and 16].

Objective(s)

- To compare the efficacy of cenegeerin vs. vehicle in Cornea and conjunctiva vital staining with fluorescein (National Eye Institute [NEI] scales) at week 4, 8, 12 and 16 by testing the superiority.
- To compare the efficacy of cenegeerin vs. vehicle in Tear Film Break-Up Time (TFBUT) at week 4, 8, 12 and 16 by testing the superiority.
- To compare the efficacy of cenegeerin vs. vehicle in SANDE scores at week 8, 12 and 16 by testing the superiority.
- To compare the efficacy of cenegeerin vs. vehicle in worsening in symptom scores (SANDE) and/or NEI score at week 4 by testing the superiority.
- To compare the efficacy of cenegeerin vs. vehicle in impact of dry eye on everyday life (IDEEL) questionnaire at week 4, 8, 12 and 16 by testing the superiority.

Endpoint(s)

- Change from baseline in Cornea and conjunctiva vital staining with fluorescein (NEI scale) [Time frame: week 4, 8, 12 and 16].
- Change from baseline in TFBUT [Time frame: week 4, 8, 12 and 16].
- Change from baseline in SANDE global scores, and for severity and frequency [Time frame: week 8, 12 and 16].
- Number of patients experienced a worsening in symptom scores (SANDE global score) and/or NEI score $\geq 50\%$ assessed at week 4.
- IDEEL questionnaire [Time frame: week 4, 8, 12 and 16].

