4.7 Eligible eye

Assuming that all the inclusion/exclusion criteria are met in both eyes, the worse eye (eligible eye) will be determined at the baseline visit using a stepladder approach, as follows:

1. Schirmer’s Test: worse eye determined as eye with lower Schirmer I score.
2. NEI score: if Schirmer I score is the same in both eyes, worse eye will be determined by NEI score (cornea + conjunctival staining).

If all the above are identical, determination of the worse eye will be based on the investigator’s judgement, otherwise the right eye will be used as the eligible eye.

5. Sample size justification

The sample size of the study is calculated based on results from previous studies.

Sample size was calculated according to the following assumptions:

- randomization ratio 1:1.
- a difference of 30% in Schirmer I rate of responders (value >10mm/5min at week 4.) in favor of rhNGF treatment at Week 4, with a responder rate of 5% for vehicle.
- 15 points in Global SANDE score improvement at Week 12, with a standard deviation of 20 points.

Based on these assumptions, a total sample size of 90 evaluable patients (100 pts considering 10% of patients not evaluable after enrollment) allows to achieve an overall power of 90% to show superiority of rhNGF eye drops solution vs vehicle in terms of both co-primary endpoints, considering a one-sided alpha of 0.025. Specifically:

- A power of 95.8% is achieved for Schirmer I primary endpoint.
- A power of 94.0% is achieved for SANDE primary endpoint.

6. Randomization and blinding

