6.1.1 Randomization

Eligible patients will be randomized in a 1:1 ratio to either cenegegermin ophthalmic solution 20 mcg/mL TID or vehicle ophthalmic solution TID.

Randomization will be stratified by site to ensure balanced assignment across treatment groups. The stratified permuted block randomization list will be generated with a computer procedure by an independent statistician not involved in the conduct of the study.

Randomization will be performed through IRS. Each Patient Kit number will be randomly associated with a treatment group. The randomization list will be provided to the facility responsible for IMP packaging/labelling for the purpose of IMP preparation. Each randomized patient will be allocated with randomization number according to the stratified randomization list. Dropouts after randomization will not be replaced

The enrollment of patients will be scheduled in order to assure an inclusion of approximately 100 patients to ensure at least 90 patients assuming up to 10% of patients not evaluable after enrollment.

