7.1 General

All patient data collected during the study will be listed by patient and site.

Appropriate descriptive statistics will be produced by treatment arms according to the nature of the variable.

For continuous data, number of observations, mean, standard deviation, median, range (minimum and maximum) and 95% confidence intervals will be presented.

For categorical data, frequency distributions and percentages with 95% confidence intervals (Wilson method) per category will be presented.

For primary analysis, the threshold for claiming statistical significance will 0.025 one-sided. For other analysis, unless otherwise specified, the significance level for statistical testing will be 0.05 and two-sided tests.

The statistical analyses (both descriptive and inferential) of some endpoints will be done on the eligible eye when applicable. Details will be provided in the statistical analysis outputs as notes.

Additional post-hoc analysis may be produced to further allow comparison between treatment and control, according to the results obtained. Any deviations from the original statistical plan (including unplanned analyses) will be documented in the CSR.

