7.5 Sub-group analyses

Subgroup analyses of primary and secondary endpoints will be performed on the following subgroups of baseline characteristics:

- Age class (\leq Median, $>$ Median).
- Race.
- Ethnicity.
- Gender.

Within each subgroup level, descriptive in nature analyses will be performed on:

- Schirmer I test.

- SANDE global, frequency and severity scores.
- NEI scale.
- TFBUT.
- IDEEL questionnaire.

at each available timepoints by means of descriptive statistics.

In case of continuous measures, analyses will be provided for baseline visit, each post-baseline visit, and their change from baseline. Comparisons between treatments will be performed using two-sample t-test (assuming unequal variances) or, if the required assumptions are not met, the two-sample Mann–Whitney U test will be used. Assumption of normal distribution of endpoints for continuous data will be assessed by a visual inspection of distribution.

In case of categorical variables, the Fisher’s Exact test will be provided in addition to summary description.

Statistical tests for interaction (between subgroup variable and treatment arm) will be performed before investigating further subgroups: analyses of primary endpoints will be performed using regression models including treatment, subgroup variable and their interaction as covariate. If the interaction between subgroup variable and treatment arm is statistically significant at 15% nominal level in at least one regression model, then subgroup analysis will be performed. Variables that may be evaluated after test for interaction are:

Variables that may be evaluated after test for interaction are:

- Region (EU, US),
- Sjögren's syndrome (primary, secondary), *where “primary” is defined as a confirmed diagnosis of Sjögren's syndrome while “secondary” as other autoimmune disease known to induce Sjögren's Dry Eye Disease,*
- Medical history,
- Concomitant medication.

Subgroup levels may be pooled to have an adequate number of subjects per strata to perform the analysis. Decision on pooling will be taken during the Blind Data Review Meeting (BDRM), before data base lock.

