If there are not enough retrieved dropouts for convergence of MI-RD regression model, a reference-based Multiple Imputation (MI) approach will be adopted to consider a missing not at random (MNAR) mechanism for missing data: imputation of values in the rhNGF arm (above step #2) will be done using the non-missing values from the control group (this approach will be referred as "Copy Reference"). This approach does not assume benefits for rhNGF in case of discontinuation and limits a post-discontinuation clinical effect to that of vehicle. The final decision on the use of the MI-RD vs Copy-Reference for this endpoint will be done at the time of the analysis and reported in the CSR.

Whether for MI-RD or Copy-Reference approach, the adjusted estimated treatment differences in proportions between cenegegermin and vehicle at week 4 will be displayed together with the corresponding two-side 95% confidence intervals and p-value.

10.1.2.2 Change from baseline in the global SANDE score at week 12

This co-primary endpoint will be analyzed by means of an Analysis of Covariance (ANCOVA) adjusting by pre-defined baseline factors (gender, age class, baseline global SANDE score as fixed effects and site as random effect) and a one-sided test will be used to test for differences between treatment groups. Rules for derivation of SANDE scores are reported in section 12.2.

For the imputation of missing data, a regression model will be created by including the baseline global SANDE score, gender, age class, and intermediate global SANDE scores up to week 12. Two hundred data sets will be generated, and the random seed number will be 37103939. MI will be implemented in the following steps:

1. Partial imputation assuming MAR will be carried out to impute intermittent (non-monotone) missing data of global SANDE score based on a multivariate joint Gaussian imputation model using the MCMC method. A separate imputation model will be used for each treatment arm. In case of non-convergence or non-estimability issues, a single imputation model will be considered (with treatment arm added as explanatory variable to the model). A total of 200 datasets will be created. These datasets will be utilized in Step #2.
2. The remaining monotone missing data will be imputed using a MI regression including the same explanatory variables of the previous step. According to MI-RD approach, only non-missing values from retrieve dropouts will be used to inform the regression model.

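### SAP 10.2.3 and the within-subgroup comparisons in SAP 7.5 are unadjusted and forgo precision that baseline adjustment would give; no planned power or confirmatory claim is affected

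*SAP*

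**What the plan says.** **Co-primary SANDE model (SAP 10.1.2.2).** This is an ANCOVA "adjusting by pre-defined baseline factors (gender, age class, baseline global SANDE score as fixed effects and site as random effect". The Schirmer logistic model in 10.1.2.1 is built the same way. Site is there for a reason (SAP 6.1.1): "Randomization will be stratified by site to ensure balanced assignment across treatment groups".

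**Secondary endpoints (SAP 10.2.3).** For continuous measures the arms are compared on visit values and on change from baseline: "Comparisons between treatments will be performed using two-sample t-test (assuming unequal variances) or, if the required assumptions are not met", by Mann-Whitney. No covariate is named. The section is labelled descriptive and covers all secondary endpoints. Those in the hierarchy of 10.2.1 also receive an adjusted test under 10.2.2.

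**Status of these comparisons.** SAP 3.2.2 sets the objective of comparing cenegermin with "vehicle in SANDE scores at week 8, 12 and 16 by testing the superiority", and words the Schirmer, NEI, TFBUT and IDEEL objectives in the same way. SAP 7.1 sets the level: "For other analysis, unless otherwise specified, the significance level for statistical testing will be 0.05 and two-sided tests".

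**Subgroups (SAP 7.5).** Within each level the same t-test or Mann-Whitney is used for continuous measures, again labelled descriptive. The interaction screen is separate: "analyses of primary endpoints will be performed using regression models including treatment, subgroup variable and their interaction as covariate". The output list in SAP 15.1 titles those models as ANCOVA or logistic regression with multiple imputation.

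**The concern.** Two groups of endpoints have no adjusted analysis anywhere in the SAP:

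- SANDE global, severity and frequency at weeks 8 and 16.
- Continuous change in Schirmer I at weeks 4, 8, 12 and 16. Protocol 9.4.3.3 had the week 8 change as the first key secondary endpoint, analysed with the adjusted primary methods. SAP 7.9 and 10.2.1 replaced it with a responder endpoint, which left the continuous measure with the 10.2.3 test alone.

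Baseline values of all these measures are collected, so adjustment needs no new data. A t-test on change uses the baseline with a fixed slope of one. That is less efficient than estimating the slope, and it leaves part of any chance baseline imbalance in the estimate. Imbalance matters most in small subgroup levels.

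There is also a reporting problem. SANDE global at week 12 appears in the key first results twice: as the adjusted co-primary (Table 14.2.1.2) and among the visit-by-visit SANDE global summaries (Table 14.2.5.2.1), to which 10.2.3 attaches an unadjusted test. The reader gets two estimates and two p-values for one endpoint and visit, and the SAP does not say how to read them together. The SANDE results at weeks 8 and 16 are likewise not on the same basis as the week 12 result.

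**Working it through.** **1. Inputs.** From SAP section 5: "randomization ratio 1:1", 90 evaluable patients (so 45 per arm), a SANDE difference of 15 points, SD 20, "considering a one-sided alpha of 0.025". The two-sided 0.05 of SAP 7.1 has the same upper critical value. A median age split of 90 gives 45 per level, so about 22 per arm. Not in the documents, and assumed here: SD 20 is the SD of the change score; equal variance at baseline and follow-up; correlation rho between them of 0.3 to 0.9; a smaller effect of 10 points as an illustration.

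**2. The SAP's own figure.** Unadjusted two-sample t-test: noncentrality = 15 / (20 × √(2/45)) = 15 / 4.216 = 3.56, with 88 degrees of freedom. Power = 94.04%, against 94.0% stated. The planned SANDE power is therefore that of an unadjusted test.

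**3. Variance ratio.** With common variance s², the change score has variance 2s²(1 − rho) and the ANCOVA residual has s²(1 − rho²). The ratio is (1 + rho)/2, so the adjusted SD is 20 × √((1 + rho)/2). The gain is measured against the change score, so the partial use of baseline in a change score is already credited.

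**4. Power (noncentral t, one degree of freedom less for the covariate).**

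| Setting | Unadjusted | rho 0.3 (ratio 0.65) | rho 0.5 (0.75) | rho 0.7 (0.85) | rho 0.9 (0.95) |
|---|---|---|---|---|---|
| 45 per arm, 15 points | 94.0% | 99.2% | 98.2% | 96.8% | 95.0% |
| 45 per arm, 10 points | 65.0% | 82.9% | 77.3% | 72.0% | 67.2% |
| 22 per arm, 15 points | 68.1% | 85.4% | 80.1% | 75.0% | 70.3% |

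The gain is about 1 to 5 percentage points in the first row, 2 to 18 in the second and 2 to 17 in the third.

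**5. Site alone.** Taking 10 sites (the protocol synopsis says approximately 10) at a cost of 9 degrees of freedom, residual variance is multiplied by (1 − ICC). The ICC is not given. At 45 per arm and 15 points, power is 94.0%, 95.0% and 95.9% for ICC 0, 0.05 and 0.10. At 22 per arm it is 67.5%, 69.8% and 72.1% against 68.1% unadjusted, so with no site effect the adjustment costs slightly more than it returns.

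**6. Schirmer.** Entry limits the baseline to 2 to 5 mm. Whole-millimetre values spread evenly over that range have SD 1.12 mm. With an assumed follow-up SD F of 5 to 10 mm and slope b of 0.5 or 1, the ratio (F² − (1.12b)²) / (F² + 1.12² − 2b × 1.12²) is 0.987 to 1.000. Adjustment gains essentially nothing there.

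**The case against.** **The analyses are descriptive.** Both sections say so, and Protocol 9.4.3.3 also treats them as descriptive, with suitable parametric tests. They lie outside the hierarchy. This stands, and it limits the point to a modest one. It does not remove it, because SAP 3.2.2 describes the same comparisons as tests of superiority and for some endpoints nothing else is planned.

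**A reader might infer that the trial loses power it was designed to have.** It does not. The 94.0% is an unadjusted figure, and no power is claimed for these analyses.

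**A reader might infer that every subgroup effect is judged by a t-test, or that the interaction screen ignores baseline.** The documents do not support either. Interactions are tested by regression. The output list calls the SANDE models ANCOVA, the SAP's own name for its baseline-adjusted co-primary model. What is true is that 7.5 names only treatment, subgroup and their interaction, so the remaining covariates are unstated. No loss of power should be attached to that.

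**A reader might infer that NEI, TFBUT and IDEEL at week 16 also have no model.** That is unclear. SAP 10.2.2.4 to 10.2.2.6 promise model-based differences at each visit, and the protocol's IDEEL model includes week 16, but the imputation models and the table titles stop at week 12.

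**A t-test on change is valid under randomisation.** Agreed: it is unbiased, and regression to the mean is expected equally in both arms. The argument is efficiency and chance imbalance, not bias.

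**The full co-primary model may not fit in small subgroup levels.** This stands. With about 22 per arm over about 10 sites, and fewer in some race or ethnicity levels, random site, gender and age class may not be estimable. The fix allows for it.

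**Conclusion.** The point holds as a matter of precision and consistency. The comparisons in SAP 10.2.3 and the within-level comparisons in SAP 7.5 omit the baseline and site terms of the co-primary models. For off-week-12 SANDE and for continuous Schirmer change, no adjusted result is planned.

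The practical gain is for SANDE: 2 to 18 percentage points of power at an assumed 10-point effect in the full sample, and 2 to 17 at 15 points in a half-sample subgroup. The upper ends need a correlation of 0.3; at 0.9 the gain is about 2 points. If the SD of 20 is already a residual SD from an adjusted model, these figures do not apply. The equal-variance assumption may also be imperfect, because entry requires a SANDE score above 25 mm. For Schirmer the gain is negligible, and site alone adds about 0 to 2 points in the full sample.

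The co-primary tests, the hierarchy and the planned power are untouched.

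**What to change.** - **SAP 10.2.3.** Make the main comparison for continuous endpoints an ANCOVA on observed data with treatment, the endpoint's own baseline, gender and age class as fixed effects and site as a random effect. Report the adjusted difference with its confidence interval, and keep the t-test or Mann-Whitney as a secondary display. Specify observed data because the SANDE imputation in 10.1.2.2 runs only to week 12. For SANDE global at week 12, state that the co-primary analysis is the result of record.
- **SAP 7.5, within levels.** Adjust at least for the endpoint's baseline. Drop site, gender or age class where it cannot be estimated or where it defines the subgroup.
- **SAP 7.5, interaction screen.** State that the models are those of 10.1.2.1 and 10.1.2.2 plus the subgroup variable and its interaction with treatment.

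The cost is SAP wording, made before unblinding, and re-programming of the affected tables: the continuous-endpoint tables in the 14.2.5 series and the subgroup tables 14.2.6.3 to 14.2.6.7, which run to several dozen. No new data are needed, and the co-primary tests and the hierarchy do not change.

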11.1 Adverse events

Adverse Events (AEs) started before administration of study treatment will be considered as pre-treatment; any AE started on or after the date of the first dose of study medication or started prior to first dose and worsened in severity after the first dose will be considered as Treatment-Emergent Adverse Event (TEAE).

In case of missing or incomplete dates not allowing a direct allocation to any of the two categories of AEs (pre-treatment/TEAE), an allocation will be done according to the available parts of the onset and the end dates (see Table 6). In case of TEAE, the event can be further classified as:

- On Treatment period, or
- On Follow-up period

according to the available parts of the onset and the end dates (see Table 6).

All AEs will be coded by SOC and PT according to MedDRA thesaurus. In addition, each AE will be graded to capture the relationship to IMP and severity (see protocol for details).

Pre-treatment AEs will be presented in the listings only.

TEAE summaries will be presented, displaying frequencies and percentages of patients reporting AEs within each SOC in decreasing order of total frequency. Along with AEs, number of events will be reported. On each of these summaries, patients will be counted only once per SOC and, within each SOC, patients will be counted only once per PT.

“Possible”, “Probable” and “Highly Probable” or missing relationships will be considered as related to study drug (ADR – Adverse Drug Reaction) for the summary tables. “None” and “unlikely” relationships will be considered not related to study drug.

The following table will be presented by treatment group and overall:

- A summary overview (patient with at least one event, percentage, and number of events) of:
 - TEAEs,
 - Ophthalmic TEAEs,
 - Non-Ophthalmic TEAEs,
 - severe TEAEs,
 - severe Ophthalmic TEAEs,
 - severe Non-Ophthalmic TEAEs,
 - serious TEAEs,
 - serious Ophthalmic TEAEs,
 - serious Non-Ophthalmic TEAEs,
 - non-serious TEAEs,
 - ADRs,
 - Ophthalmic ADRs,
 - Non-Ophthalmic ADRs,
 - serious ADRs,
 - TEAEs leading to discontinuation of IMP,
 - TEAEs leading to discontinuation of study,
 - TEAEs leading to death.

The following tables will be presented by treatment group:

- Summary of Ophthalmic TEAEs by primary SOC and PT and by study period (on treatment/follow-up and overall).
- Summary of Non-Ophthalmic TEAEs by primary SOC and PT and by study period (on treatment/follow-up and overall).
- Summary of TEAEs by primary SOC, PT and Severity.
- Summary of Serious TEAEs by Primary SOC and PT and by study period (on treatment/follow-up and overall).
- Summary of ADRs by Primary SOC and PT and by study period (on treatment/follow-up and overall).
- Summary of ADRs by Primary SOC and PT and Severity.
- Summary of TEAEs leading to IMP Discontinuation by Primary SOC and PT and by study period (on treatment/follow-up and overall).
- Summary of TEAEs leading to study Discontinuation by Primary SOC and PT and by study period (on treatment/follow-up and overall).
- Summary of TEAEs leading to Death by Primary SOC and PT.
- Listing of Deaths.

12. Derivations and date conventions

